**Protocol Version:**

Protocol Version 8

10/04/25

Study objectives:

1. To assess the feasibility of delivering the Strathclyde Sleep Intervention to adolescents with co-morbid insomnia and mental health attending a mental health services. The following feasibility benchmarks will be assessed: recruitment and retention, participant attendance, staff training, intervention fidelity and participant adherence.
2. To examine participant acceptability. The researchers will conduct qualitative interviews with the participants and delivery staff to examine the acceptability of the programme.
3. To investigate the preliminary effectiveness by assessing the following: sleep parameters, insomnia symptoms, Circadian phase preference (baseline only) and mental health symptoms. Data will be collected at baseline, post-intervention and 3-month follow-up.

Methods:

Design – The study will assess the feasibility, acceptability, and preliminary effectiveness of the intervention using a single-arm repeated measures design. Data to assess the feasibility objectives and benchmarks will be collected throughout. Acceptability will be explored via qualitative interviews following the delivery of the intervention. Outcomes will be measured at baseline, immediately post-treatment and at 3-month follow-up.

Participants - We intend to assess the feasibility of recruitment of adolescents from mental health services, therefore no formal power calculation has been conducted for this study. We aim to recruit up to 40 adolescents and up to 10 members of staff. This estimate was based on previous research conducted within adolescents in mental health services (Åslund et al., 2020; Bradley et al., 2018; Clarke et al., 2015; Palermo et al., 2017; Rollinson et al., 2021). The results of this study will inform sample size calculations for future RCT of the Strathclyde Sleep Intervention.

Eligibility criteria –

***Inclusion criteria:***

1. Adolescents aged 12-18 years

2. Meeting thresholds for insomnia disorder (determined by cut-off scores on the Sleep Condition Indicator (2) - <2 indicates probable insomnia, Luik et al., 2019)
3. Receiving support for mental health
4. Able to engage with intervention protocol

***Exclusion criteria:***

1. Active suicide ideation and/or recent suicidal attempts
2. Contraindications for components of CBT-I (sleep restriction therapy) including seizure disorders/conditions including epilepsy, bipolar disorder, symptoms of psychosis, obstructive sleep apnea and parasomnias.
3. Diagnosis of Autism Spectrum Disorder, Attention Deficit Hyperactivity Disorder, Foetal Alcohol Spectrum Disorder (Neurodiversity)
4. Those who are currently completing, or have recently completed (in the past 6 months), CBT-I for insomnia elsewhere (or components of CBT-I including e.g. sleep restriction therapy, stimulus control, cognitive techniques). This will only include in-person, one-to-one methods of delivery.

Procedure - Staff will be identified by the service management and volunteer to receive training. We intend to train up to 10 members of staff to deliver the intervention. Staff will receive training, will be offered ongoing supervision (provided by the research team), and will utilize the intervention delivery manual to deliver the intervention. A list of common FAQs will also be provided to support the delivery. Staff within the service will use a referral form (accessible via Qualtrics) to assess eligibility and refer potential participants, they will also be responsible for sharing the participant information sheet and video link. Adolescents and caregivers will be advised that the researcher will be in contact with them in 2-3 working days to arrange a time to meet on Zoom. During the meeting, the researcher will re-check eligibility to ensure nothing has changed since the referral form was completed, to answer any questions and to obtain verbal consent. The adolescents and caregivers will also be sent a URL link to the written consent form (accessed online via Qualtrics). Written consent will be obtained from adolescents and parents/caregivers. Forms will inform participants about their right to withdraw from the intervention and/or data collection/analysis at any time, until the end of the follow-up assessment.

After receiving a signed consent form, participants will be sent an email with a link to complete a baseline assessment questionnaire. The participants will also be asked to complete a sleep diary for up to 2-weeks before the delivery of the Strathclyde Sleep Intervention. Participants will be invited to attend 4 weekly sessions for the delivery of the intervention. Trained staff will deliver the intervention to small groups of adolescents (up to 6). All sessions will be audio recorded. The participants will be asked to complete a sleep diary for the duration of the intervention. This will take approximately 2-3 minutes to complete and is necessary to ensure the sleep window can be appropriately titrated during sleep restriction therapy. Following the delivery of the intervention, all participants will be asked to complete the post-intervention assessment (questionnaire, 2-week sleep diary), and will be invited to attend semi-structured interviews with a member of the research team to explore the acceptability of the intervention. The staff will also be invited to attend semi-structured interviews to explore the acceptability of training, delivery, and future implementation. Staff will be asked to read an information sheet and provide informed consent prior to the interview. Interviews will be conducted following the completion of post-intervention assessments and will be audio-recorded. Three months following completion of the post-intervention assessment, the participants will be asked to complete the follow-up assessment (questionnaire, 2-week sleep diary). This will be the end of their participation in the study.

Data analysis plan - To examine the feasibility of delivering the intervention to adolescents attending mental health services, we will examine recruitment and retention rates, attendance logs and adherence to intervention components using frequencies and descriptive statistics. An intervention fidelity checklist will also be created, and the researchers will score the delivery of the intervention against the checklist. Qualitative data will be transcribed verbatim and analysed using Braun and Clarke's (2006) method of thematic analysis to examine acceptability. To examine preliminary effectiveness, we will compare changes in sleep parameters, insomnia and mental health symptoms from baseline, post-intervention and follow-up using mixed modelling analysis.

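### Group, digital, self-help or remote CBT-I taken during the study is permitted by exclusion 4 and not described in the analysis, so its effect after baseline is credited to the intervention

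*Combined protocol and SAP*

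**What the plan says.** Item 4 of the exclusion criteria removes "Those who are currently completing, or have recently completed (in the past 6 months), CBT-I for insomnia elsewhere", and extends this to components of CBT-I. Its last sentence then narrows the rule: "This will only include in-person, one-to-one methods of delivery".

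The study's own intervention is a group programme. Under Procedure: "Trained staff will deliver the intervention to small groups of adolescents (up to 6" per group.

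Under Methods, Design, the study will assess "preliminary effectiveness of the intervention using a single-arm repeated measures design". The Data analysis plan states: "we will compare changes in sleep parameters, insomnia and mental health symptoms from baseline, post-intervention and follow-up using mixed modelling analysis". It names no covariate, subgroup or sensitivity analysis for other sleep treatment. The measures listed under the third study objective cover sleep, insomnia, circadian preference and mental health, but not other treatment.

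Two further provisions matter. Inclusion item 2 requires a current insomnia-range score on the Sleep Condition Indicator. The last assessment is late enough for other treatment to begin in the meantime: "Three months following completion of the post-intervention assessment, the participants will be asked to complete the follow-up assessment".

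**The concern.** The protocol treats current or recent CBT-I as a reason to exclude, then admits every format except one. The admitted formats include group delivery, which is the format under study. Item 4 also operates only at entry, so CBT-I of any kind begun later falls outside it.

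A randomised comparison would spread outside CBT-I across the arms. Here there is no comparator, and the estimate of effectiveness is the change over time itself. Improvement after baseline that is due to an outside programme cannot be told apart from improvement due to the intervention. The Participants paragraph says the results will inform the sample size of a later randomised trial, so the estimate may be used again.

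**Working it through.** **Which adolescents can enter.** Reading item 4 with its last sentence:

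- In-person, one-to-one CBT-I, current or in the past 6 months: excluded.
- Group, digital, self-help or remote one-to-one CBT-I, current or in the past 6 months: not excluded by item 4.

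**What each exposure does to change from baseline.**

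- *Concurrent outside CBT-I.* Benefit that arises after baseline enters the post-intervention and follow-up scores but not the baseline score. It adds to the observed change.
- *CBT-I completed in the past 6 months.* Benefit already gained is in the baseline score and is not counted as change. These adolescents enter only if they still meet the insomnia cut-off. Carry-over that continues after baseline would add to the change. A baseline already improved, or earlier non-response, could reduce it. The sign is not determined.

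**Size for concurrent use.** There is no figure in the plan to reproduce: it states that no power calculation was done and gives no SD, effect size or dropout. Let f be the share of participants with concurrent outside CBT-I and d the change it adds after baseline, in SD units of the outcome. If effects add:

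observed mean change = intervention and all other causes + f × d

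Inputs: n = 40, the upper limit under Methods, Participants ("We aim to recruit up to 40 adolescents and up to 10 members of staff"). Both f (5% to 25%, or 2 to 10 of 40) and d (0.3 to 0.8) are assumptions.

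| Exposed of 40 | f | d = 0.3 | d = 0.5 | d = 0.8 |
|---|---|---|---|---|
| 2 | 0.05 | 0.015 | 0.025 | 0.04 |
| 4 | 0.10 | 0.03 | 0.05 | 0.08 |
| 8 | 0.20 | 0.06 | 0.10 | 0.16 |
| 10 | 0.25 | 0.075 | 0.125 | 0.20 |

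**Comparison with sampling error.** With equal SDs at the two time points and pre-post correlation r (assumed 0.3 to 0.7), the 95% half-width of a mean change is 1.96 × √(2(1 − r)/n). At n = 40:

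- r = 0.7: 1.96 × √(0.6/40) = 0.24 SD
- r = 0.5: 1.96 × √(1.0/40) = 0.31 SD
- r = 0.3: 1.96 × √(1.4/40) = 0.37 SD

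Even the largest shift in the table, 0.20 SD, is smaller than the narrowest half-width, 0.24 SD. The shift is systematic, however, so a confidence interval does not reflect it.

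**Cost of a sensitivity analysis.** Removing 10 of 40 widens intervals by √(40/30) = 1.155, about 15%, before attrition. Removing 2 of 40 widens them by √(40/38) = 1.026, about 3%.

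**The case against.** The strongest reply is that the last sentence of item 4 is an explicit decision, probably made to protect recruitment, and that a feasibility study may admit a broad population. That stands. The entry rule is not an error, and the point does not ask for it to change.

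Second, a reader might infer that the exposure goes unrecorded. The documents do not support that. The referral form and questionnaires are not reproduced, and staff who apply item 4, like the researcher who re-checks eligibility, must ask about CBT-I and how it was delivered. Much of the entry information may therefore be elicited already. What can be said is that the text describes neither keeping nor analysing it, and describes no enquiry after entry.

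Third, a reader might infer that treatment finished before entry is also counted as intervention effect. It is not: that benefit is in the baseline score, and continuing insomnia is required.

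Fourth, the magnitude is wholly assumed. Adding the effects is itself an assumption, and a doubtful one, because outside CBT-I would overlap with the intervention in content such as sleep restriction. The figures then lean high.

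Fifth, recording CBT-I does not give a single-arm study causal attribution. Natural course, regression to the mean after selection on a cut-off, and the mental health support required for entry all remain. That stands too. The fix removes one avoidable ambiguity and no more.

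Last, effectiveness is preliminary and the third objective, and the documents do not say that the pre-post effect will be the input to the later sample size. This limits the importance of the point but does not remove it.

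**Conclusion.** The concern holds for concurrent outside CBT-I in formats that item 4 does not cover. Improvement which that treatment causes after baseline is credited to the Strathclyde intervention, because there is no comparator and no described analysis of the exposure. For recent completers the direction is uncertain.

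Under the assumed shares and effects, the shift in mean change is about 0.015 to 0.20 SD, and less if effects are not additive. If no such adolescents enrol it is zero; the documents do not say how many would.

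The documents do not support the stronger inferences that the eligibility rule is mistaken or that the study's findings as a whole are compromised. Feasibility and acceptability do not depend on this attribution, although earlier CBT-I could colour adherence and acceptability. This is a cheap improvement of modest importance.

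**What to change.** Leave the entry rule as it is and make three additions.

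1. **Record the exposure.** On the referral form or at baseline, record CBT-I of any format: none, past 6 months, or ongoing. On the post-intervention and 3-month questionnaires, record any CBT-I started since baseline, in any format including one-to-one. If the forms already hold such an item, the plan need only say so and state how it will be used.
2. **Pre-specify the reporting.** Give each change from baseline for all participants as the main analysis, and again without those who had ongoing outside CBT-I at baseline. Treat past-6-month users as a further sensitivity set.
3. **Describe later starts only.** Report CBT-I begun after baseline as counts by format and time point, and do not exclude on it. Starting other treatment may reflect non-response, so dropping those adolescents could inflate the apparent effect.

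The cost is one item on existing forms, and wider intervals in the sensitivity analysis only (about 15% if 10 of 40 are set aside). Eligibility and recruitment are unaffected.

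### The baseline questionnaire follows consent with no limit on the interval to session 1, so any symptom change during a wait enters the single-arm pre-post estimate

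*Combined protocol and SAP*

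**What the plan says.** All timing statements are in the Procedure text of the combined protocol and SAP.

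- **Questionnaire:** once the signed consent form is in, "participants will be sent an email with a link to complete a baseline assessment questionnaire".
- **Diary:** participants are also asked to "complete a sleep diary for up to 2-weeks before the delivery of the Strathclyde Sleep Intervention".
- **Delivery:** "Trained staff will deliver the intervention to small groups of adolescents (up to 6"), and "Participants will be invited to attend 4 weekly sessions for the delivery of the intervention".

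The design statement under Methods describes assessing "preliminary effectiveness of the intervention using a single-arm repeated measures design". For effectiveness, the Data analysis plan says "we will compare changes in sleep parameters, insomnia and mental health symptoms from baseline, post-intervention and follow-up using mixed modelling analysis".

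The documents do not cap the interval from questionnaire to session 1, repeat the questionnaire before session 1, or plan to record the interval or adjust for it. The Zoom re-check described under Procedure concerns eligibility and is part of the consent step, so it does not renew the outcome baseline.

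**The concern.** The two baseline measures have different anchors. The diary is tied to the start of delivery. The questionnaire is tied only to consent. If a group takes time to assemble, a participant's questionnaire may describe a period some weeks before treatment, and the gap may differ between members of the same group.

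In a controlled trial, drift over that gap would be expected in both arms and would largely cancel. Here the change from baseline is the whole effectiveness estimate, so nothing separates drift from response. Two features of the Inclusion criteria make drift plausible: entry requires a score below a Sleep Condition Indicator cut-off, and every participant is already receiving mental health support. The Participants paragraph says the results will inform the sample size of a future randomised trial, so a distorted change score could carry forward.

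**Working it through.** The plan states no interval, accrual rate, power or effect size, so there is no figure of its own to reproduce. The check has three parts.

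**1. Which outcomes are exposed.** The analysis names sleep parameters, insomnia symptoms and mental health symptoms. Sleep parameters would ordinarily come from the diary, which is anchored to delivery. Insomnia and mental health symptoms would ordinarily come from the questionnaire, which is not. The exposure is therefore confined to the questionnaire outcomes.

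**2. How long a wait could be.** From the documents: groups of at most 6, four weekly sessions, and "We aim to recruit up to 40 adolescents and up to 10 members of staff". That implies at least 40/6, rounded up, = 7 groups if recruitment reaches its maximum. Assumed: r consents per week, evenly spaced, and a group of g that starts when its last member consents.

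- Longest wait = (g − 1)/r weeks.
- Mean wait = (g − 1)/(2r) weeks.
- Share of the wait-plus-delivery interval = mean wait/(mean wait + 4), taking delivery as about 4 weeks.

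| g | r per week | Longest wait (weeks) | Mean wait (weeks) | Share |
|---|---|---|---|---|
| 6 | 0.5 | 5/0.5 = 10 | 5 | 5/9 = 56% |
| 6 | 1 | 5/1 = 5 | 2.5 | 2.5/6.5 = 38% |
| 6 | 2 | 5/2 = 2.5 | 1.25 | 1.25/5.25 = 24% |
| 6 | 3 | 5/3 = 1.7 | 0.83 | 0.83/4.83 = 17% |
| 4 | 1 | 3/1 = 3 | 1.5 | 1.5/5.5 = 27% |

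If the two-week diary starts only after the group is full, 2 weeks are added to each wait. For g = 6 and r = 1 the share becomes 4.5/8.5 = 53%.

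**3. How much regression to the mean re-timing could remove.** Let D be the distance of the selected participants' entry scores from the mean, in SD. Let ρ be the correlation between the selecting score and a later measurement of the same scale. The expected distance remaining at that later measurement is ρD. Moving the baseline from the present questionnaire date to just before session 1 therefore removes

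D × (ρ at present questionnaire date − ρ just before session 1).

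Assume that ρ falls from 0.8 to 0.7 over the wait and that D is 1 to 1.5:

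- D = 1: 1 × (0.8 − 0.7) = 0.10 SD.
- D = 1.5: 1.5 × (0.8 − 0.7) = 0.15 SD.

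This applies to the scale used for selection. Mental health symptoms are not selected on a score, so the formula does not apply to them directly, and the size of their drift is unknown.

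**The case against.** **The wait is inferred.** The consent wording fixes an order (no data before consent) and does not say the link goes out at once. At the two later time points the questionnaire and diary are listed as one package, so issuing them together before delivery is a possible reading of the baseline too. Six is a ceiling on group size and is not stated as a condition for starting. All of this stands: the documents do not show that anyone waits for a group to fill. It does not close the gap, because the text as written permits an interval of any length.

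**A larger figure is tempting.** A reader might apply (1 − ρ) × D with ρ from 0.7 to 0.8 and infer a bias between 0.2 × 1 = 0.20 SD and 0.3 × 1.5 = 0.45 SD. That is the total regression from the selecting score. Eligibility is assessed at referral and re-checked at the Zoom meeting, both before the questionnaire, so part of the regression has already happened by then. The range is not what re-timing would remove.

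**Re-timing is not free.** A reader might suppose that people lost before session 1 supply no change data. However, the Procedure asks all participants for the post-intervention assessment, so a non-attender could still contribute, and a baseline-only record also informs a mixed model. Baseline symptoms also help describe who is lost, which bears on retention. These points stand, and the fix is shaped to meet them.

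**The aim is preliminary.** The study is about feasibility, and no stated progression rule rests on the change score. This limits the weight of the point. Effectiveness is nevertheless the third stated objective and has its own planned model.

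**Conclusion.** The point holds as an inexpensive improvement to the assessment schedule. The questionnaire baseline has no upper limit on its distance from session 1, and a single arm cannot separate change over that interval from change under treatment. The affected estimates are those for insomnia and mental health symptoms.

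The size is unknown. The illustrative mean wait of 2.5 weeks (longest 5) rests on an assumed one consent per week into a group of 6 that starts when full. The 0.10 to 0.15 SD for the selection score rests on the assumed correlations and entry distances above.

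Two stronger readings are not supported. A reader might infer that benefit is necessarily overstated, but drift could also be a worsening that masks benefit, and the documents give no evidence on its direction. A reader might also infer that the whole effectiveness analysis is compromised, but the diary is already anchored to delivery.

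**What to change.** Change the trigger in the Procedure text:

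- Send the insomnia and mental health symptom questionnaire together with the baseline diary once the group start date is set. It should be completed within the pre-delivery diary window and before session 1.
- Send it to every consented participant, whether or not they later attend.
- Collect demographics, eligibility items and circadian preference at consent.
- Record and report the days from questionnaire to session 1, including for any participants already enrolled.

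The cost is a revised sentence and a different email trigger. No assessment is added. Participants who withdraw before the group date is set would have no baseline symptom score beyond the referral eligibility information, though they stay in the recruitment and retention counts. A later deadline also carries some risk of missing baselines.

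The change does not remove natural recovery or regression to the mean during delivery and follow-up. Those remain because there is no control group, and the report should say so.

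### Does an adolescent who misses the post-intervention assessment fall out of the 3-month follow-up and the interviews?

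*Combined protocol and SAP*

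**What the plan says.** In the combined protocol and SAP, the Procedure section gives the order of events after the four sessions. The post-intervention assessment comes first: "Following the delivery of the intervention, all participants will be asked to complete the post-intervention assessment (questionnaire, 2-week sleep diary". The same sentence extends the interview invitation to all adolescents. After two sentences about staff interviews, the section adds: "Interviews will be conducted following the completion of post-intervention assessments and will be audio-recorded". The follow-up is then timed: "Three months following completion of the post-intervention assessment, the participants will be asked to complete the follow-up assessment (questionnaire, 2-week sleep diary".

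The Design paragraph under Methods places the interviews more loosely: "Acceptability will be explored via qualitative interviews following the delivery of the intervention". It lists a 3-month follow-up without saying when the three months begin.

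Three other statements bear on the point. The feasibility benchmarks in the first objective are "recruitment and retention, participant attendance, staff training, intervention fidelity and participant adherence". The Data analysis plan handles them descriptively: "we will examine recruitment and retention rates, attendance logs and adherence to intervention components using frequencies and descriptive statistics". The consent wording in Procedure separates two kinds of withdrawal, giving a "right to withdraw from the intervention and/or data collection/analysis at any time".

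No visit window, fallback date or definition of a completed assessment is given.

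**The concern.** The only stated start for the three months is an event that may not happen. An adolescent can leave the post-intervention questionnaire or diary undone and still be in the study, because missing an assessment is not withdrawal from data collection. On the literal text that adolescent never becomes due for follow-up.

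If the study were run that way, measured retention would fall because of a scheduling rule and not because adolescents were unwilling to respond. Three-month outcomes would be lost from people who might have supplied them. The results are meant to inform sample size for a later randomised trial, so a retention figure lowered in this way could carry forward.

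Two further worries go with this. The assessment has two parts, so the three months might be counted from either. And if an interview needs a completed assessment, the acceptability material would come mainly from the more engaged adolescents.

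**Working it through.** The plan gives no retention figure, non-completion rate or power calculation, so there is nothing to reproduce. The check is a reading of the text followed by conditional arithmetic.

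**1. Who is asked to do the follow-up.** The follow-up sentence refers to the participants in general, not to those who completed the previous assessment. The Design paragraph plans the 3-month measurement without restriction. The text omits a date for non-completers; it does not exclude them.

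**2. Who is interviewed, and when.** The invitation sentence reads: "all participants will be asked to complete the post-intervention assessment (questionnaire, 2-week sleep diary), and will be invited to attend semi-structured interviews". It attaches no condition about completing the assessment. The later sentence on interview timing follows directly after the staff interviews and naturally covers both groups. Staff have no post-intervention assessment, so for them it can only mean that interviews come after that phase of the study. Its plural noun fits that reading. It sets a sequence, which agrees with the Design paragraph.

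**3. Which part counts as completion.** The assessment is defined as a questionnaire plus a 2-week diary. If both are done, it is complete when the later one is done. If only one is done, there is one date, not two competing ones. Choosing the earlier part for a full completer would move the date by at most about 14 days, or 14/91 = 15.4% of three months taken as 91 days, but that is not the natural reading.

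**4. Size of the loss if non-completers were not approached.** Let *m* be the share missing the post-intervention assessment, *r* the share of those who would return a follow-up if asked, and *u* the share of those not approached. Loss of retention = *m* × *r* × *u*. None of the three is in the documents.

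| Assumed *m* | Number of 40 | Assumed *r* | Loss at *u* = 1 | Loss at *u* = 0 |
|---|---|---|---|---|
| 0.15 | 6 | 0.20 | 1.2 returns, 3 points | 0 |
| 0.35 | 14 | 0.40 | 5.6 returns, 14 points | 0 |
| 0.10 | 4 | 0.20 | 0.8 returns, 2 points | 0 |
| 0.30 | 12 | 0.40 | 4.8 returns, 12 points | 0 |

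The result depends on *u*. For *u* to be 1, staff would have to treat a missing date as an instruction not to make contact, and nothing in the plan says that.

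**5. What a different anchor would do.** Take three months as 13 weeks (91 days), with the diary starting straight after the last session.

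- Present rule: a prompt completer is due 2 + 13 = 15 weeks after the last session. With completion 0 to 4 weeks late (assumed), this becomes 15 to 19 weeks. The interval from completed assessment to follow-up request stays at 13 weeks.
- Fixed date for all, at last scheduled session + 2 weeks + 3 months: every adolescent is due at 15 weeks. If the assessment may be up to 7 days late, the interval between assessments can shrink to 91 − 7 = 84 days (7/91 = 7.7%). With a ±14-day follow-up window as well, it runs from 91 − 7 − 14 = 70 to 91 + 14 = 105 days, a departure of up to 21/91 = 23.1%. Of those 21 days, 7 come from the change of anchor and 14 from the window.

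Each rule holds one interval steady and lets the other vary.

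**The case for a change.** The strongest case for a change is that the gap is real, bears on a named benchmark and costs a sentence or two to close. Non-completers who have not withdrawn can still be approached. The planned mixed model can use a follow-up value from someone with no post-intervention value, but only if that person was asked. Relying on good sense leaves the date to each researcher, and two researchers could choose differently.

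Part of this stands. The plan gives no fallback date for an adolescent who misses the post-intervention assessment, and a protocol could have included one. What does not stand is the step from a missing date to missing data. The sensible reading is to send the follow-up to everyone not withdrawn from data collection, about three months after the post-intervention assessment period, and to record when it was returned. Different choices by different researchers would shift the timing for a few adolescents in a study whose feasibility results are descriptive. They would not remove those adolescents from the retention count.

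The worry about hearing from disengaged adolescents is fair as a matter of qualitative sampling, but all of them are already invited. Seeking out low attenders, or tabulating interview uptake by attendance, would be an extra and not a repair.

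**Conclusion.** The concern does not call for a change. What is left of it is an unstated fallback date for adolescents who miss the post-intervention assessment, a detail that those running the study would fill sensibly. The interview part does not hold: all adolescents are invited after delivery, and the timing sentence sets an order. The supposed 14-day ambiguity is weak, because a two-part assessment is complete when its later part is done.

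The loss of 3 to 14 percentage points of retention (2 to 12 under the lower non-completion range) rests on two assumed rates and on non-completers not being approached. With ordinary contact of everyone still in the study, it is zero. Re-anchoring all participants would trade a steady interval between assessments for a steady time since treatment. In a single-arm feasibility study of up to 40 adolescents with no power calculation, either choice is defensible.
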